The number of patients prematurely censored will be summarised by treatment arm together with baseline prognostic factors of the prematurely censored patients. A patient is defined as prematurely censored if they did not progress and the latest scan prior to DCO was more than one scheduled tumour assessment interval (+ 2 weeks) prior to the DCO date.

In addition, duration of follow-up will be summarised using median time from randomisation to date of censoring (date last known to be non-progressor) in censored (not progressed) patients only, presented by treatment group. The interquartile range will also be presented by treatment group.

As patients will be randomised, imbalances in demographic factors between the treatment groups are not anticipated. However, if any imbalances should occur, the HR and associated CI calculated from a Cox Proportional Hazards model containing treatment, the stratification variable and these additional demographic variables, may be reported.

Summary statistics will be provided for the PFS events due to death and those due to RECIST progression, and also for censored events. In addition, the reason for censoring across treatment arms will be provided. In the case where the distribution of discrepancy in progression assessment between BICR and local investigator across treatment groups is not similar, the PFS analysis may be biased due to informative censoring. The potential impact of informative censoring on parameter estimate will be assessed through sensitivity analysis,

using either the methods of Jackson et al or Hsu and Taylor (Jackson et al 2014, Hsu and Taylor 2009) when considering time dependent covariates. This work will be presented separately and will not form part of the CSR.

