Attrition bias will be assessed by repeating the primary PFS analysis except that the actual PFS event times, rather than the censored times, of subjects who progressed or died in the absence of progression immediately following two, or more, non-evaluable tumour assessments will be included. In addition, subjects who take subsequent therapy prior to their last evaluable RECIST assessments or progression or death will be censored at their last evaluable assessment prior to taking the subsequent therapy. Additionally a KM plot of the time to censoring where the censoring indicator of the primary PFS analysis is reversed (what was originally a censored event in the primary PFS analysis becomes an actual event and what originally was a PFS event becomes a censored event) will be presented.

(c) Ascertainment bias

A stratified log-rank test will be repeated using BICR RECIST data to programmatically derive PFS. The HR and 95% CI will be presented.

The type of event (RECIST or death) will also be provided.

If there is an important discrepancy between the primary analysis using investigator assessments and this sensitivity analysis using BICR assessments, then the proportion of subjects with site but no central confirmation of progression will be summarised. This scenario is possible as at the time of the primary analysis data cut off all scans will be sent for central review assessment regardless of whether or not a patient has been assessed as having progressed by the site. The approach of imputing an event at the next visit in the BICR assessed analysis may help inform the most likely HR value, but only if an important discrepancy exists.

Disagreements between investigator and BICR assessment of RECIST progression will be presented for each treatment group. The summary will include the early discrepancy rate which is the frequency of BICR progressions declared before the investigator review progressions (≥2 weeks earlier and including progressions declared by BICR but not investigator) as a proportion of all BICR progressions, and the late discrepancy rate which is the frequency of BICR progressions declared after the investigator review (≥2 weeks later and including progressions declared by investigator but not BICR as a proportion of all discrepancies (including early and late discrepancies) (Amit et al 2011).

(d) Deviation bias (if meaningful to do)

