4.2.4 Overall survival (OS)

OS data will be analysed at the time of the primary analysis of PFS and will use the same methodology and model (provided there are sufficient events available for a meaningful analysis [≥20 deaths], if not descriptive summaries will be provided). A further interim analysis of OS will be performed when ~206 events are observed (approximately 53% maturity of the 391 patients randomised) and a final analysis of OS will be performed when the OS data are approximately 60% mature (~235/391 patients randomised).

An additional descriptive analysis for OS will also be performed at 7 years post the last patient randomised as part of global enrolment (DCO March 2022).

As a key sensitivity, the analysis of OS will be repeated in those patients whose gBRCAm status is confirmed by Myriad centrally. A KM plot of OS in this subset of patients will be presented by treatment group. This sensitivity analysis will also be repeated excluding any patients who did not have a tBRCA mutation status confirmed by Foundation Medicine.

The remaining sensitivity analyses outlined for PFS in Section 4.2.2 will not be repeated for OS with the exception of a KM plot of the time to censoring where the censoring indicator of the primary OS is reversed (what was originally a censored event in the primary PFS2 analysis becomes an actual event and what originally was a PFS2 event becomes a censored event).

A summary of survival status at the time of analysis will be produced. This will summarise the number of patients who have died, who are still in survival follow-up, who are lost to follow-up or who have withdrawn consent.

In addition, duration of follow-up will be summarised using medians:

- In censored (not died) patients only: Time from randomisation to date of censoring (date last known to be alive)
- In all patients: Time from randomisation to the date of death or to the date of censoring for censored patients.

At the time of the last analysis of OS, the subgroup analyses and global interaction test detailed for PFS in Section 4.2.2 will be repeated for OS.

Exploratory analyses of OS

Exploratory analyses of OS adjusting for impact of subsequent PARP inhibitor trial or treatment may be performed if a sufficient proportion of patients switch. The decision to adjust and final choice of methods will be based on a blinded review of the data and the plausibility of the underlying assumptions. Baseline and time-dependent characteristics will

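### The all-patients median in SAP 4.2.4 understates OS follow-up; the reversed-indicator Kaplan-Meier curve already planned gives the right figure at no cost

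*SAP*

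**What the plan says.** For PFS, SAP 4.2.2 summarises duration of follow-up as a median, with interquartile range, from randomisation to the "date of censoring (date last known to be non-progressor) in censored (not progressed) patients only". This summary is specified separately for each arm.

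For OS, SAP 4.2.4 gives two medians under the same label of duration of follow-up. The first leaves out everyone who has died: "In censored (not died) patients only: Time from randomisation to date of censoring (date last known to be alive". The second keeps the deaths in and counts each of them up to the day of death: "In all patients: Time from randomisation to the date of death or to the date of censoring for censored patients". The OS text does not say whether either median is shown by arm.

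The SAP also plans the curve that estimates potential follow-up. For PFS it is a "KM plot of the time to censoring where the censoring indicator of the primary PFS analysis is reversed" (SAP 4.2.2, attrition bias). For OS it is a "KM plot of the time to censoring where the censoring indicator of the primary OS is reversed" (SAP 4.2.4). No median is taken from either curve. Related checks are planned for PFS: "The number of patients prematurely censored will be summarised by treatment arm", and reasons for censoring are tabulated across arms.

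**The concern.** Duration of follow-up should describe how long patients could have been observed. The all-patients OS median is the median of the smaller of death time and censoring time, so it falls as more patients die. If half of an arm has died before the shortest potential follow-up is reached, the figure equals that arm's median survival and says nothing about follow-up.

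The OS analyses fall in that region: about 206 and 235 deaths among 391 patients, and a descriptive analysis seven years after the last patient was randomised. A reader of the 7-year update could conclude that follow-up was much shorter than it was. If the figure is shown by arm, the same reader could conclude that placebo patients were followed less well. A censored-only median also depends on who has had the event, because patients with long potential follow-up are more likely to have had the event and drop out of the calculation.

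**Working it through.** **Anchor to the plan's own figure.** The documents give no follow-up figure, so the design inputs were checked first. For a hazard ratio of 0.62, two-sided 5%, 90% power and 2:1 allocation, Schoenfeld's formula gives (1.960 + 1.282)² / [(2/3)(1/3)(ln 0.62)²] = 206.9, that is 207 events against 206 stated in SAP 1.3. With 206 events the power is 0.899. The olaparib median is 13/0.62 = 21.0 months, matching the stated 8-month gain.

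**Inputs.** From the documents: OS hazard ratio 0.85; 18-month recruitment; PFS cut-off about 36 months after the first patient, or at the latest 36 months after the last (36 + 18 = 54); 7-year OS cut-off at 84 + 18 = 102 months; patients confirmed alive censored at the data cut-off (SAP 3.2.3). Assumed: uniform accrual (the SAP says only that it is non-linear), exponential OS, placebo OS median 75 to 90 months, and the loss rates below.

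**Formulae, no loss.** Let D be the cut-off, λ the event rate, S(t) = exp(−λt), and G(t) the chance that potential follow-up exceeds t. G(t) is 1 up to D − 18 and (D − t)/18 after that, the same in both arms.

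- All-patients median: solve S(t)G(t) = 0.5.
- Censored-only median: D − 18 − ln[(1 + e^(−18λ))/2]/λ.
- Reverse Kaplan-Meier median: solve G(t) = 0.5, giving D − 9. It does not involve S, so the treatment effect cannot move it.

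**OS at 102 months, all patients.** True and reverse Kaplan-Meier follow-up is 102 − 9 = 93 months in both arms. Take a placebo median of 75 months:

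- Placebo: S(75) = 0.5 and G(75) = 1, so the figure is 75.0, which is simply median survival (75.2 by simulation).
- Olaparib: at t = 84.5, S = 2^(−0.85 × 84.5/75) = 0.515 and G = 17.5/18 = 0.972; the product is 0.50, so the figure is 84.5.

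The chance of death by the cut-off is 1 − (e^(−84λ) − e^(−102λ))/(18λ) = 0.576 on placebo and 0.518 on olaparib. That gives 391 × (0.576 + 2 × 0.518)/3 = 210 deaths, close to the planned 206.

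| Assumed placebo median (months) | Deaths of 391 | Olaparib | Placebo | Gap |
|---|---|---|---|---|
| 75 | 210 | 84.5 | 75.0 | 9.5 |
| 80 | 201 | 85.2 | 80.0 | 5.2 |
| 85 | 193 | 85.7 | 84.1 | 1.6 |
| 90 | 185 | 86.2 | 84.7 | 1.5 |

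Against 93 months, the understatement runs from about 7 months (93 − 86.2) to 18 months (93 − 75.0).

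**OS at 102 months, censored only.** With the 75-month placebo median, λ = 0.00924 (placebo) and 0.00786 (olaparib). The formula gives 84 + 8.63 = 92.6 and 84 + 8.68 = 92.7, against 93. The gap is 0.1 month. With an assumed 0.3% monthly loss it is 0.2 to 0.3 month.

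**PFS at 36 months, censored only.** With λ = ln 2/13 = 0.0533 (placebo) and 0.62 × 0.0533 = 0.0331 (olaparib), the formula gives 18 + 6.9 = 24.9 and 18 + 7.7 = 25.7. Reverse Kaplan-Meier gives 27.0 in both arms. Back-loaded accrual (entry time 18√U, U uniform) gives 22.2 and 22.6, against 23.3. When censoring is placed on the 12- and 24-weekly scan dates, the gap disappears if there is no dropout.

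**PFS at 54 months with an assumed 1% monthly loss, equal in both arms.** Simulation gives censored-only medians of about 31.5 (olaparib) and 17.0 (placebo). Reverse Kaplan-Meier gives about 40.4 in both; as a check, e^(−0.01 × 40.5) × (54 − 40.5)/18 = 0.667 × 0.750 = 0.50. At 36 months the same loss rate gives a gap of only 0.7 to 1.5 months.

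**The case against.** A good deal can be said for the plan, and most of it stands.

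- The OS censored-only median, listed first in SAP 4.2.4, is nearly right, because most censoring is at the data cut-off. A reader might infer that every follow-up summary in the SAP is badly biased. That is not so.
- A reader might also infer that the SAP sets out OS follow-up by arm and so builds in a false imbalance. Only the PFS median is specified by arm.
- The reversed-indicator curves are planned for both endpoints, so the SAP does not lack the right method. It lacks one number from it.
- The primary PFS analysis was done before this SAP was dated: SAP section 5 describes an OS update agreed after it. No further PFS analysis is planned unless health authorities ask.
- The documents define maturity as events over patients. Follow-up medians trigger no analysis and enter no test.
- The gap between arms in the all-patients figure depends on an assumed placebo median and is small (1.5 months) at 90 months.

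What these points leave untouched is that the all-patients OS median is labelled duration of follow-up. It falls short of 93 months by roughly 7 months or more in every scenario tabulated, whether or not it is shown by arm. Its definition is stated openly, but a careful label does not turn it into a measure of follow-up.

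**Conclusion.** The point holds as a reporting improvement, chiefly for one OS summary. At the 7-year cut-off the all-patients median is about 84.5 (olaparib) and 75 (placebo) months with an assumed placebo median of 75, and 86.2 and 84.7 with 90, when potential follow-up is 93 months in both arms. This rests on uniform 18-month accrual, exponential survival, the documents' hazard ratio of 0.85 and no loss. If shown by arm, it can suggest an imbalance that does not exist.

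The censored-only medians are much less affected: about 0.1 month between arms for OS without loss and under 1 month for PFS at 36 months with administrative censoring only. Serious distortion needs a late cut-off together with substantial dropout, and the documents state no dropout rate. The stronger claim, that these summaries will generally make equally followed arms look different, is not supported. Nor is any suggestion that the efficacy result is affected: the hazard ratio, log-rank test, power and alpha are unchanged.

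**What to change.** For the OS analyses still to come, and for any PFS update that health authorities request, define duration of follow-up as the median and interquartile range, by arm and overall, from the reversed-indicator Kaplan-Meier curve already planned. Relabel the OS all-patients median as observed time. The censored-only medians can stay as secondary descriptions.

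While editing SAP 4.2.4, correct the parenthesis that explains the reversed OS indicator, which refers to PFS2 rather than OS.

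The cost is a sentence in each section and reading quantiles from a curve that will be produced anyway. No new data, alpha or analysis timing is involved.

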The number of patients prematurely censored will be summarised by treatment arm together with baseline prognostic factors of the prematurely censored patients. A patient is defined as prematurely censored if they had not progressed and the latest scan prior to DCO was more than one scheduled tumour assessment interval (+ 2 weeks) prior to the DCO date.

Subgroup analyses will be conducted comparing PFS between treatments in the following subgroups of the full analysis set:

- Response to previous platinum chemotherapy (clinical complete response or partial response)

- ECOG performance status at baseline (0 or 1)
- Baseline CA-125 value (\leq ULN vs $>$ ULN)

- Age at randomisation (<65 vs. ≥ 65)
- Stage of disease at initial diagnosis (III or IV)

A minimal number of patients that are tBRCAm *and* gBRCA wt are expected to be randomised into this study. Assuming the number of progression events in this population is less than 20, these patients will be summarised with a Kaplan Meier of PFS by treatment. If the number of events is ≥ 20 , this factor will be added to the forest plot (i.e. gBRCA and tBRCA mutated vs tBRCA mutated only).

Other baseline variables may also be assessed if there is clinical justification. For each subgroup, the HRs (olaparib: placebo) and associated CIs will be calculated from a Cox proportional hazards model (ties = Efron) that contains the treatment term, factor (subgroup) and treatment-by-factor interaction term. The treatment effect HRs for each treatment comparison along with their confidence intervals will be obtained for each level of the subgroup from this single model. The HRs and 95% CIs will be presented on a forest plot including the HR and 95% CI from the overall population (using the primary analysis).

The purpose of the subgroup analyses is to assess the consistency of treatment effect across potential or expected prognostic factors. The results observed in Phase II (D0810C00019) do not suggest that these factors will be predictive factors for a qualitatively different treatment effect.

If there are too few events available for a meaningful analysis of a particular subgroup (where there are less than 20 events per subgroup level no formal statistical tests will be performed), the relationship between that subgroup and PFS will not be formally analysed. In this case, only descriptive summaries will be provided.

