5	INTERIM ANALYSES	
6	CHANGES OF ANALYSIS FROM PROTOCOL	
7	REFERENCES	74
LIST (OF TABLES	
Table 1	Summary of Outcome Variables and Analysis Populations	21
Table 2	TL Visit Responses	24
Table 3	NTL Visit Responses	28
Table 4	Overall Visit Responses	29
Table 5	Health-Related Quality of Life	37

Date 15 February 2022

Date 15 1 columny 2022		
Table 6	Health-Related Quality of Life : Change rates - overall score	38
Table 7 Formal Statistical Analyses to be Conducted and Pre-Planned Sensitivity Analyses		48
LIST OF FIG	URES	
Figure 1	Study Flow Chart Up to 108 Weeks on Treatment	17
Figure 2	Study Flow Chart At 108 Weeks on Treatment	18
Figure 3	Example of Dose Intensity Calculations for Olaparib	42
Figure 4	Multiple Testing Procedure	51

LIST OF ABBREVIATIONS

The following abbreviations and special terms are used in this study Statistical Analysis Plan.

Abbreviation or special term	Explanation	
AE	Adverse event	
ALT	Alanine aminotransferase	
AST	Aspartate aminotransferase	
Baseline	Refers to the most recent assessment of any variable prior to dosing with study treatment	
BD	Twice daily	
BICR	Blinded independent central review	
BoR	Best overall RECIST response	
BP	Blood pressure	
BRCA	Breast cancer susceptibility gene	
BRC Analysis ®	Gene sequencing and large rearrangement analysis for Hereditary Breast and Ovarian Cancer, registered trademark of Myriad Genetics, Inc	
BRCA mutation or BRCAm	Breast cancer susceptibility gene mutation (see gBRCA mutation or gBRCAm)	
CA-125	Cancer Antigen – 125	
cfDNA	Circulating free DNA	
CLIA	Clinical Laboratory Improvement Amendments	
CCR	Clinical complete response. 'Response' is used throughout the protocol and refers to patients being, in the opinion of the investigator, in clinical complete response or partial response on the post-treatment scan. Clinical complete response is defined as no evidence of either RECIST measurable or non-measurable disease on the post-treatment scan and a normal CA-125. Partial response is defined as ≥30% reduction in tumour volume demonstrated from the start to finish of chemotherapy OR no evidence of RECIST measurable disease on the post-treatment scan with a CA-125 which has not decreased to within the normal range.	
CI	Confidence interval	
CR	Complete response	
CRF / eCRF	Case Report Form (electronic)	
CRO	Clinical Research Organisation	
CSP	Clinical Study Protocol	

Abbreviation or special term	Explanation	
CSR	Clinical Study Report	
CT	Computed tomography	

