4.2.2 Primary variable - progression free survival (PFS)

PFS will be analysed using a log-rank test stratified by response to first line platinum chemotherapy (in the opinion of the investigator, clinical complete response (CR) or partial response (PR)) for generation of the p-value and using the Breslow approach for handling ties. The hazard ratio (HR) and confidence interval (CI) will be estimated from a Cox Proportional Hazards model (with ties = Efron and the stratification variable as a covariate) and the CI will be calculated using a profile likelihood approach.

Stratification variables will be defined according to data from the randomisation. If there are any patients who were mis-stratified, a sensitivity analysis will be carried out using the (correct) baseline data collected in the eCRF. Although not anticipated, if patients are

randomised in error when they have not previously had a response to first line platinum chemotherapy, they will be categorised in the "PR" category for the sensitivity analysis using eCRF stratification data.

The HR (olaparib versus placebo) together with its corresponding 95% CI and p-value will be presented (a HR less than 1 represents the reduction in risk for those patients allocated olaparib).

A KM plot, with tick marks to identify censored observations, of PFS will be presented by treatment group. Summaries of the number and percentage of subjects experiencing a PFS event, and the type of event (RECIST or death) will be provided along with median PFS and corresponding 95% CI for each treatment.

The assumption of proportionality will be assessed. Note that in the presence of non-proportionality, the HR will be interpreted as an average HR over the observed extent of follow-up. Proportionality will be tested firstly by producing plots of complementary log-log (event times) versus log (time) and, if these raise concerns, a time dependent covariate would be fitted to assess the extent to which this represents random variation. The primary analysis will be based on the PFS based on investigator assessments, and using all scans regardless of whether they were scheduled or not.

The proportion and corresponding 95% CI of patients alive and progression free at 6 monthly intervals will be summarised (using the KM plot) and presented by treatment group.

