Subgroup analyses will be conducted comparing PFS between treatments. Median PFS will be reported. The purpose of the subgroup analyses is to assess the consistency of treatment effect across potential or expected prognostic factors. The results observed in Phase II (D0810C00019) do not suggest that these factors will be predictive factors for a qualitatively different treatment effect. If there are too few events available for a meaningful analysis of a particular subgroup (where there are less than 20 events per subgroup level no formal statistical tests will be performed), the relationship between that subgroup level and PFS will not be formally analysed. In this case, only descriptive summaries will be provided. When there are less than 20 events per a subgroup, consideration will be given to combing relevant subgroups if appropriate to do so.

The following subgroups of the full analysis set will be analysed for PFS:

- Response to previous platinum chemotherapy (obtained from the randomisation schedule)
- gBRCAm status-confirmed by Myriad test or gBRCAwildtype (wt) or gBRCA variant of uncertain significance (VUS) or missing by Myriad test]*. This will be determined from the Myriad central laboratory tests.
- ECOG performance status at baseline (normal activity [PSTAT=0] or restricted activity [PSTAT=1]).

This will be determined from the response to "Performance status" (PSTAT module) on the eCRF at screening.

• Baseline CA-125 value (\leq ULN or > ULN).

The baseline CA-125 value will be defined as the measurement nearest to but prior to date of randomisation.

• BRCA mutation type (BRCA1 or BRCA2 or BRCA1/2 (both)).

This will be determined from the Myriad central laboratory tests. If there are less than 20 events in the "BRCA1/2 both" category, these patients will be excluded from this analysis.

• Age ($<65 \text{ or } \ge 65$).

Date 15 February 2022

This will be determined from the date of birth (BIRTHDAT in the DEM module) and date of randomization. See section 4.2.13 for rules on deriving age for partial dates of birth.

• Stage of disease at initial diagnosis (III [FIGO_STG=30 or 31 or 32 or 33] or IV [FIGO_STG=40]).

This will be determined from the response to "FIGO stage" (PATHGEN module) on the eCRF at screening.

 Residual macroscopic disease following debulking surgery prior to entry into the study [HISPOUT=1] or no residual macroscopic disease [HISPOUT=2].

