For each subgroup, the HRs (olaparib: placebo) and associated CIs will be calculated from a Cox Proportional Hazards model (ties = Efron) that contains the treatment term, factor (subgroup) and treatment-by-factor interaction term. The treatment effect HRs for each treatment comparison along with their CIs will be obtained for each level of the subgroup from this single model. The HRs and 95% CIs will be presented on a forest plot including the HR and 95% CI from the overall population (using the primary analysis). In addition, summaries of the number and percentage of patients experiencing a PFS event for each subgroup will be provided along with the median PFS for each treatment.

No adjustment to the significance level for testing will be made since all these subgroup analyses will be considered exploratory and may only be supportive of the primary analysis of PFS.

The presence of quantitative interactions will be assessed by means of an overall global interaction test. This will be performed in the overall population by comparing the fit of a Cox Proportional Hazards model including treatment, all covariates, and all covariate-by-treatment interaction terms, with one that excludes the interaction terms and will be assessed at the 2-sided 10% significance level. If a covariate does not have ≥20 events per level (of the covariate) it will be included as a covariate in the model but the covariate-by-treatment interaction term will be omitted. If the fit of the model is not significantly improved then it will be concluded that overall the treatment effect is consistent across the subgroups.

If the global interaction test is found to be statistically significant, an attempt to determine the cause and type of interaction will be made. Stepwise backwards selection will be performed on the saturated model, whereby (using a 10% level throughout) the least significant interaction terms are removed one-by-one and any newly significant interactions re-included until a final model is reached where all included interactions are significant and all excluded interactions are non-significant. Throughout this process all main effects will be included in the model regardless of whether the corresponding interaction term is still present. This approach will identify the factors that independently alter the treatment effect and prevent identification of multiple correlated interactions.

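### Most subgroup Cox models omit the one randomisation stratum that the overall HR on the same forest plot adjusts for: a minor mismatch that costs little to remove for OS

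*SAP*

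**What the plan says.** SAP 4.2.2 estimates the overall PFS hazard ratio from a Cox model "with ties = Efron and the stratification variable as a covariate". That variable is clinical complete response (CR) or partial response (PR) to first line platinum, the only factor by which randomisation is stratified.

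For subgroups, the same section uses one Cox model per factor, which "contains the treatment term, factor (subgroup) and treatment-by-factor interaction term". Protocol 12.2.2 specifies a model "that contains the treatment term, factor (subgroup) and treatment-by-factor interaction term". Neither lists the stratum, and neither says why it is left out. The subgroup estimates are then "presented on a forest plot including the HR and 95% CI from the overall population (using the primary analysis").

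Two rows are special:
- One listed subgroup is "Response to previous platinum chemotherapy (obtained from the randomisation schedule"), so that row's model contains the stratum as its own factor.
- Baseline CA-125 (at or below versus above ULN) overlaps the stratum, because the SAP abbreviations list defines clinical complete response as "no evidence of either RECIST measurable or non-measurable disease on the post-treatment scan and a normal CA-125".

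For survival, SAP 4.2.4 states that, at the last OS analysis, "the subgroup analyses and global interaction test detailed for PFS in Section 4.2.2 will be repeated for OS".

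**The concern.** The stated purpose of the subgroup analyses is to judge whether the effect is consistent. A reader does this by looking along the forest plot from the overall estimate to each row. Here the overall estimate and most rows come from models with different adjustment sets, so part of any gap between them is technical.

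Two mechanisms are at work:
- **Attenuation.** A Cox model that omits a prognostic covariate gives an HR nearer 1 than the same model with it. Poor-prognosis patients fail first, and faster on placebo. The patients still at risk on placebo therefore become relatively favourable, and the apparent effect shrinks over time.
- **Chance imbalance.** Stratified randomisation balances CR and PR between arms across the whole trial. It does not guarantee balance within an ECOG, stage, BRCA-type or region subgroup, and the subgroup model does not correct for any imbalance.

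What is at stake is how a supportive display is read, for PFS and again for final OS. No confirmatory claim depends on it.

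**Working it through.** **1. The plan's own figure.** SAP 1.3 and protocol 12.3 give 206 PFS events for 90% power, HR 0.62, two-sided 5% and 2:1 allocation. By Schoenfeld's formula, events = (1.960 + 1.282)² / [(2/3)(1/3)(ln 0.62)²] = 10.51 / (0.2222 × 0.2285) ≈ 207. The figure reproduces.

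**2. Inputs for the attenuation.** From the documents: true HR 0.62, placebo median 13 months, exponential PFS, 2:1 allocation. Assumed, because the documents do not give them: PR share 20-50%, PR:CR hazard ratio 1.5-3.0, and administrative censoring uniform over 18-36 or 36-54 months.

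**3. Method.** The large-sample limit β of the model without the stratum solves the expected score equation

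∫ { dN₁(t) − [e^β W₁(t) / (e^β W₁(t) + W₀(t))] dN(t) } = 0,

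where W_a(t) is the expected share at risk in arm a, averaged over CR and PR, and N counts expected events. With the stratum in the model, the limit is 0.620 in every scenario. Without it (the two figures are for the shorter and longer censoring windows):

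| PR:CR hazard ratio | PR share 20% | PR share 35% | PR share 50% |
|---|---|---|---|
| 1.5 | 0.624, 0.625 | 0.625, 0.627 | 0.626, 0.628 |
| 2.0 | 0.631, 0.633 | 0.635, 0.639 | 0.636, 0.641 |
| 3.0 | 0.647, 0.648 | 0.657, 0.663 | 0.658, 0.669 |

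The shift toward 1 runs from 0.6238/0.62 − 1 = 0.6% to 0.6686/0.62 − 1 = 7.8%. At an illustrative true HR of 0.31 it runs from about 1% to 17%.

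For OS, where both documents illustrate with HR 0.85, a rough scaling of the worst case gives ln 0.6686 / ln 0.62 = 0.84, then 0.85^0.84 = 0.872, a shift of about 2.6%. This borrows the PFS assumptions and only indicates scale.

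**4. Direction relative to the overall HR.** Each subgroup model conditions on its own factor, which the overall model omits. With PR share 30%, factor share 40%, no correlation between them, true HR 0.62 and the longer censoring window:

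| Stratum effect | Factor effect | Overall (stratum only) | Subgroup rows | Rows relative to overall |
|---|---|---|---|---|
| 2.0 | 1.0 | 0.620 | 0.637 | nearer 1 |
| 1.5 | 1.5 | 0.627 | 0.626 | about equal |
| 1.5 | 2.0 | 0.640 | 0.626 | further from 1 |

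The gap can go either way.

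**5. Chance imbalance.** In a simulation of 391 patients (PR share 20-25%, PR:CR hazard ratio 1.5-3, all assumed), adding the stratum moved a subgroup HR based on about 70-90 events by more than 10% in 3-39% of runs. It removed an average attenuation of about 1-6%. Root mean squared error barely changed. In a subgroup of about 51-53 events simulated alone (PR share 20-35%), the adjusted and unadjusted HRs differed by more than 10% in 21-29% of runs at a PR:CR hazard ratio of 1.5, 32-37% at 2.0 and 51-60% at 3.0.

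**6. Scale against sampling error.** The approximate 95% CI multiplies or divides a subgroup HR by exp(1.96/√(2e/9)) at e events: 2.53 at 20 events (the SAP's minimum per level), 1.71 at 60 and 1.52 at 100. The average shift in step 3 is well inside these.

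**The case against.** The strongest reply is that this is a deliberate choice, stated identically in both documents, and that little depends on it. The subgroup analyses are declared exploratory. Levels of a factor are compared with each other inside one common model. The formal consistency conclusion comes from a global interaction test that fits treatment, all covariates and all their interactions together. Platinum response is a listed factor, so that test carries the stratum. The average shift is small beside the confidence intervals. Finally, SAP section 5 refers to the PFS analysis as already done, so changing its subgroup models now would be post hoc.

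Most of this stands, and it makes the point minor. It does not explain why the rows and the overall estimate use different adjustment sets. Exploratory status justifies the absence of alpha control, not a different model. The global test does not produce the estimates that readers see on the plot. The timing argument applies to PFS but not to the last OS analysis, which was still to come at the SAP date.

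A reader might infer that every subgroup HR will sit on the null side of the overall HR. The documents do not support that: the platinum-response row contains the stratum, the CA-125 row partly carries it, and step 4 shows that the other rows can fall on either side. A reader might also infer that the rows cannot be compared with the overall HR at all. At shifts of this size that is too strong; they are not like-for-like.

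**Conclusion.** The mismatch is real, appears in both documents and is unexplained. Relative to the same subgroup model with the stratum, most subgroup HRs are attenuated by roughly 1-8% at HR 0.62, and chance CR/PR imbalance within subgroups is left uncorrected. The range rests on assumed values for PR share, PR:CR hazard ratio and follow-up. A shift near 17% needs both an HR of about 0.31 and a PR:CR hazard ratio of 3. At an OS effect near 0.85 the shift would be smaller than at 0.62.

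The primary log-rank test, the primary HR, the sample size and the global interaction test are untouched. Adjustment brings little gain in overall accuracy; its value is that the rows and the overall estimate rest on the same stratum adjustment. This is a minor improvement at very low cost.

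**What to change.** - **OS, and any PFS update that health authorities request.** State in SAP 4.2.4, with a matching sentence in 4.2.2, that every subgroup model includes response to first line platinum (randomisation value) as a covariate, except the model in which it is the subgroup factor. Record this in SAP section 6 as a difference from protocol 12.2.2.
- **The completed PFS forest plot.** Keep the pre-specified version. Either add a stratum-adjusted version as a supplement, or footnote that the overall HR is adjusted for the stratum and the subgroup HRs are not, apart from the platinum-response row.

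The cost is one extra parameter per model and a declared difference between the OS subgroup models and the PFS models already run. In the CA-125 row the added term will do little in the elevated level, where by definition nearly all patients should be PR.
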